5.2 Exclusion Criteria

Patients are to be excluded from the study if they meet any of the following criteria:

1. Patient has a known history of HIV or active hepatitis B or active hepatitis C infection (testing not mandatory)
2. Patient has any of the following cardiac abnormalities (as determined by treating MD):
 - a. Myocardial infarction within six months prior to registration,
 - b. New York Heart Association Class III or IV heart failure ([Appendix III](#)) or known left ventricular ejection fraction (LVEF) < 40%, as assessed by echocardiogram or MUGA scan;
 - c. A history of familial long QT syndrome;
 - d. Symptomatic atrial or ventricular arrhythmias not controlled by medications
 - e. $QTc \geq 470$ msec calculated from a mean of 3 ECG readings using Fridericia's correction ($QTcF = QT/RR^{0.33}$). *Note:* Patients with $QTcF \geq 470$ msec and with bundle branch block and/or pacemaker rhythm may be enrolled after approval by Medical Monitor;
3. Concomitant malignancies or previous malignancies with less than a 1-year disease free interval at the time of signing consent. Patients with adequately resected basal or squamous cell carcinoma of the skin, or adequately resected carcinoma *in situ* (e.g. cervix) may enroll irrespective of the time of diagnosis
Prior exposure to azacitidine, decitabine or investigational hypomethylating agent, or induction chemotherapy for MDS or AML. *Note:* intensive chemotherapy for any other prior cancer is *not* exclusionary.
4. Use of cytotoxic chemotherapeutic agents, or experimental agents (agents that are not commercially available) for the treatment of MDS within 14 days of the first day of study drug treatment
5. Concurrent use of erythroid stimulating agents, G-CSF, or GM-CSF within 14 days of the first day of study drug treatment.
6. History of allogeneic stem cell transplantation
7. Pregnancy: Pregnant women are excluded from this study because APR-246 has not been studied in pregnant patients. Because there is an unknown but potential risk for adverse events in nursing infants secondary to treatment of the mother with APR-246, breastfeeding should be discontinued if the mother is treated with APR-246.
8. Active uncontrolled infection.

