6.2 Criteria for Treatment, Retreatment and Dose Modifications

6.2.1 APR-246

This section outlines the requirements for proceeding with treatment with APR-246, and the protocol rules for APR-246 dose modification due to toxicity.

The

Table **4** describes the routine ECG requirements from screening through Cycle 4 for patients in Experimental Arm:

Table 4. ECG Requirements in Experimental Arm

Time Point	ECG, n	Timing
Baseline/Screening	Triplicate	Within 28 days of Cycle 1 Day 1
Cycle 1, Days 1-4	Triplicate	Pre-dose; Post dose (6 hrs. after start of infusion; ± 30 min)
Cycles 2+, Day 1	Triplicate	Pre-dose

At screening (baseline), 12-lead ECGs should be collected in triplicate to confirm QT interval does not exceed 470 msec. QT interval must be calculated from a mean of all three ECG readings using Fridericia's correction ($QTcF = QT/RR^{0.33}$).

During Cycle 1 ECG should be collected in triplicate prior to infusion of APR-246 and at the end of infusion of APR-246 (6 hours after start of infusion, ± 30 min) on Days 1 - 4. QTcF must be calculated from a mean of all three ECG readings to confirm it does not exceed 470 msec.

If a pre-dose ECG shows $QTcF \geq 470$ msec, the QTc reading should be confirmed by manual assessment using Fridericia's correction ($QTcF = QT/RR^{0.33}$). Serum concentrations of electrolytes should be monitored and corrected, if necessary. Additionally, concomitant medication should be reviewed and adjusted, if necessary. ECG may be repeated at any time, including the same day. APR-246 may only be administered when QTcF has returned to < 470 msec. If APR-246 is given on the same day, procedures outlined in the Schedule of Study Evaluations (Table 8) must be followed. If APR-246 cannot be administered on the same day, that dose must be omitted from the cycle.

If there is a significant change in QTcF, defined as either: a) increase > 60 msec from baseline (or pre-dose), or b) increase to an absolute value ≥ 501 msec, i.e. consistent with NCI CTCAE Grade 3 QTc prolongation, QTc prolongation must be confirmed by a manual assessment of the ECG, and using Fridericia's correction ($QTcF = QT/RR^{0.33}$). If confirmed, the therapy should be interrupted until a cause (electrolyte disorders or an effect of a concomitant medication) has been identified and addressed, and QTcF has returned to < 470 msec. If all other causes for clinically significant QT interval prolongation are excluded, APR-246 must be permanently discontinued.

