During subsequent cycles ECG should be collected in triplicate prior to infusion of APR-246 on Day 1 of each cycle. QTcF must be calculated from a mean of all three ECG readings to confirm it does not exceed 449 msec. If pre-dose QTcF is 450-469 msec, APR-246 may be administered, and additional triplicate ECG should be performed at the end of infusion (6 hours after start of infusion, ± 30 min). If post-dose ECG shows a significant change in QTcF, defined as either: a) increase > 60 msec from baseline (or pre-dose), or b) increase to an absolute value ≥ 501 msec, i.e. consistent with NCI CTCAE Grade 3 QTc prolongation, QTc prolongation must be confirmed by a manual assessment of the ECG, and using Fridericia's correction ($QTcF = QT/RR^{0.33}$). If confirmed, the therapy should be interrupted until a cause

(electrolyte disorders or an effect of a concomitant medication) has been identified and addressed, and QTcF has returned to < 470 msec. If all other causes for clinically significant QT interval prolongation are excluded, APR-246 must be permanently discontinued. If QTcF is unchanged or there is no significant change, additional ECG is not required during that cycle.

If repeated QTcF measurements show a stable QTcF < 450 msec, or if QTcF remains stable within the interval of 450 – 469 msec with no significant change at the end of infusion during several cycles of treatment, reducing the number of ECGs performed in the study may be discussed with the Medical Monitor.

If a patient starts treatment with another medication known to prolong QT interval at any time during the study therapy, an additional pre- and post-dose (6 hours after start of infusion, ± 30 min) ECG should be performed on the next treatment day. For patients who do not tolerate the protocol-specified dosing schedule, one dose level reduction is permitted (Table 5) in order to allow the patient to continue the study treatment. A second dose reduction could be permitted following discussion with the Sponsor and Medical Monitor.

Table 5. APR-246 Dose Levels

Dose Modification	APR-246 Dose
Starting Dose Level (DL)	APR-246 4.5 g/day 1.5 g (for first 45 minutes) + 3.0 g (for 5 hours 15 minutes)
One dose level reduction (DL-1)	APR-246 4.0 g/day 1.33 g (for first 45 minutes) + 2.67 g (for 5 hours 15 minutes)
Second dose level reduction (DL-2)*	APR-246 3.5 g/day 1.16 g (for first 45 minutes) + 2.34 g (for 5 hours 15 minutes)

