8.4 ECG in Experimental Arm: ECG for APR-246

Table 10 describes the routine ECG requirements from screening through cycle 4:

Table 10. ECG Requirements in Experimental Arm

Time Point	ECG, number	Timing
Baseline/Screening	Triplicate	Must be within 28 days of C1D1
Cycle 1, Days 1-4	Triplicate	Pre-dose; Post dose (6 hrs. after start of infusion; ± 30 min)
Cycles 2+, Day 1	Triplicate	Pre-dose

If repeated QTcF measurements show a stable QTcF < 450 msec, or if QTcF remains stable within the interval of 450 – 469 msec with no significant change at the end of infusion during several cycles of treatment, reducing the number of ECGs performed in the study may be discussed with the Medical Monitor.

If a patient starts treatment with another medication known to prolong QT interval at any time during the study therapy, an additional pre- and post-dose (6 hours after start of infusion, ± 30 min) ECG should be performed on the next treatment day.

Please consult Section 6.2.1 for additional requirements for proceeding with treatment with APR-246.

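### The eligibility Note admits bundle-branch-block or paced patients with QTcF at or above 470 msec, but Section 6.2.1 bars APR-246 at that reading with no matching exception

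*Combined protocol and SAP*

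**What the plan says.** **Entry.** Criterion 2e in Section 5.2, repeated in the synopsis, excludes a mean triplicate QTcF of 470 msec or more. The Note beneath it says that patients at or above 470 "msec and with bundle branch block and/or pacemaker rhythm may be enrolled after approval by Medical Monitor".

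**Screening, as described in Section 6.2.1.** At baseline, "12-lead ECGs should be collected in triplicate to confirm QT interval does not exceed 470 msec". The Note is not mentioned.

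**Dosing in Cycle 1.** Tables 4 and 10 require triplicate ECGs before the dose on each of Days 1 to 4. Section 6.2.1 adds: "QTcF must be calculated from a mean of all three ECG readings to confirm it does not exceed 470 msec". A pre-dose reading of 470 msec or more must be confirmed manually, electrolytes and concomitant medication are reviewed, and the ECG may be repeated. Then: "APR-246 may only be administered when QTcF has returned to < 470 msec". Failing that: "If APR-246 cannot be administered on the same day, that dose must be omitted from the cycle".

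**Dosing from Cycle 2.** One pre-dose triplicate ECG is scheduled, on Day 1. "If pre-dose QTcF is 450-469 msec, APR-246 may be administered", with an extra ECG at the end of infusion. The text does not say what follows a Day 1 reading of 470 msec or more.

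**Related text.** The interruption rules in Section 6.2.1 and the restart rule in Section 6.2.3 both require a return below 470 msec. Section 8.4 adds no exception and refers back: "Please consult Section 6.2.1 for additional requirements for proceeding with treatment with APR-246".

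**Analysis.** Under Section 9.2 the primary efficacy population is ITT, meaning all randomized patients.

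**The concern.** Entry and dosing use the same cut-off and the same Fridericia correction, but only the entry rule has an exception. A site that follows both can randomize a patient to a drug it must then withhold. The dosing rule speaks of QTcF having returned below 470 msec, which presumes a starting value below it. Patients who enter under the Note start at or above it.

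Two things are at stake. The first is patient handling: Section 2.8.1 lists QTc prolongation among the potential risks of APR-246, and on whether these patients may receive it the protocol gives two answers. The second is the comparison. Only APR-246 is gated by the ECG, so the conflict operates in one arm. An affected patient could receive azacitidine alone and still be analysed as experimental, which pulls the CR difference toward zero. Such a patient could enter the efficacy-evaluable set only through the progression route, since that set otherwise requires a completed cycle of APR-246 and azacitidine.

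**Working it through.** **Step 1: does any text carry the exception into dosing?** Take a patient enrolled under the Note, randomized to the experimental arm, whose QTcF remains at or above 470 msec.

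| Place | What it gives this patient |
|---|---|
| 5.2 and synopsis, Note to 2e | May be enrolled, with Medical Monitor approval |
| 6.2.1, screening ECG | Limit of 470 msec; no exception |
| 6.2.1, Cycle 1 Days 1–4 | Dose only below 470 msec, otherwise omit; no exception |
| 6.2.1, Cycle 2 onward | Express permission up to 469 msec; silent at 470 or more |
| 6.2.1 and 6.2.3, interruption and restart | Resume below 470 msec; no exception |
| End of Table 6, clinical judgment clause | Concerns dose modifications for toxicity; does not mention QTcF |
| 6.2.1 and 8.4, Medical Monitor's stated QT role | Discussing fewer ECGs; nothing on dosing above the limit |

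No row supplies the exception, and no alternative QT measure is given for conduction defects or pacing. The Medical Monitor's approval in 2e covers enrolment only.

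**Step 2: reproduce the plan's sample size.** Inputs from Section 9.1: CR 50% versus 25%, two-sided alpha 0.05, power 90%, 77 per arm. With pooled variance and no continuity correction, mean rate 0.375:

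n per arm = [1.960 × √(2 × 0.375 × 0.625) + 1.282 × √(0.50 × 0.50 + 0.25 × 0.75)]² / 0.25² = (1.342 + 0.848)² / 0.0625 ≈ 76.7, rounded up to 77.

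Power at 77 per arm is 0.901 by this normal approximation. It is 0.906 by exact enumeration of the same pooled z-test, counting rejections in favour of APR-246. The stated 90% is reproduced. Both calculations ignore the age stratification.

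**Step 3: illustrate the dilution.** Assumption: k of the 77 experimental patients receive no APR-246 and respond at the control rate. The experimental CR rate becomes 0.50 − 0.25 × k/77.

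| Undosed patients | Experimental CR | Power, approximation | Power, exact |
|---|---|---|---|
| 0 | 50.0% | 0.901 | 0.906 |
| 1 | 49.7% | 0.894 | 0.899 |
| 2 | 49.4% | 0.886 | 0.892 |
| 5% of arm (about 4) | 48.8% | 0.871 | 0.877 |
| 10% of arm (about 8) | 47.5% | 0.834 | 0.842 |

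The documents give no frequency, so every row below the first is an assumption. The last two rows only show how numerous such patients would have to be before power fell noticeably.

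**The case against.** The defence has four good points.

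First, a reader might infer that these patients can never be dosed. The documents do not say so. Section 6.2.1 provides for manual confirmation, electrolyte correction, medication review and repeat ECGs on the same day, so a patient close to the limit, or with a second contributing cause, could fall below it. That a conduction-related QTcF cannot fall is a clinical premise from outside the text.

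Second, a reader might infer that Days 1 to 4 are omitted in every cycle. Daily pre-dose ECGs are scheduled only in Cycle 1. Later cycles have a routine ECG on Day 1 only, and the Cycle 2 text states no consequence at 470 msec or more. The general dosing sentence may be read to apply there too, but that is inference.

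Third, entry under the Note needs Medical Monitor approval for each patient. The Medical Monitor may notice the dosing rule and decline. This limits the numbers but leaves the two texts in conflict.

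Fourth, the power loss is small at one or two patients, and the bias runs toward no difference, so it does not raise the risk of a false positive.

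The cardiac safety overview (Section 2.6.6) is redacted and may explain the intent of the Note. The operative dosing rules in Section 6.2.1 are visible, however, and they contain no exception. These points narrow the consequences; none of them reconciles the Note with Section 6.2.1.

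**Conclusion.** The contradiction holds. The Note permits enrolment at QTcF of 470 msec or more with bundle branch block or pacemaker rhythm. Section 6.2.1 withholds APR-246 at that reading, restates the limit at screening without the exception, and from Cycle 2 expressly permits dosing only up to 469 msec. For an experimental-arm patient whose QTcF stays at or above 470 msec, the Cycle 1 APR-246 doses would be omitted, later dosing has no stated permission, and the patient remains in the experimental arm for the ITT analysis.

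The statistical effect is probably small: about 0.89 instead of 0.906 with two undosed patients, assuming they respond at 25%. A reader might take this as a material threat to power, but the documents give no frequency to support that. Nor do they support describing these patients as having the most dangerous repolarisation, or predicting that sites will dose outside the rule. The point rests on conflicting instructions for a drug whose administration depends on QTcF.

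**What to change.** Reconcile the Note to criterion 2e, in Section 5.2 and the synopsis, with the 470 msec rules for screening, dosing, interruption and restart in Section 6.2.1, the Cycle 2 onward text there, the restart rule in Section 6.2.3, and Section 8.4. Entry and dosing rules should treat bundle branch block and paced rhythm in the same way, and the Cycle 2 text should say what follows a Day 1 reading at or above the limit. Which passage changes is for the sponsor to decide; this review does not choose between the rules.

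The cost is an amended sentence or two, with no increase in sample size. The downside is that a few patients may become ineligible, or that an exception has to be written and justified.

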5.3 Inclusion of Women, Minorities and Children

This study is open to both male and female patients of all ethnicities. This study excludes patients aged < 18 years.

5.4 Withdrawal Criteria

Protocol therapy will be discontinued at any time if any of the following situations occur:

1. Clinically significant progressive disease
2. The development of toxicity which, in the Investigator's judgment, precludes further therapy.
3. Patient refusal
4. A pattern of noncompliance with study medication or protocol-required evaluations and follow-up visits
5. Intercurrent illness: a condition, injury, or disease unrelated to cancer in the opinion of the investigator, that renders continuing treatment unsafe or regular follow-up impossible
6. At the discretion of the Investigator that it is in the best interest of the patient to withdraw
7. Pregnancy
8. Study termination by the sponsor

5.4.1 Withdrawn Subjects

When a patient is removed from the study, the Investigator will clearly document the reason in the medical record and complete the appropriate CRF page describing the reason for discontinuation. In addition, every effort should be made to complete the appropriate assessments listed in Section 7.5.

5.5 Noncompliance

All instances of noncompliance and all resulting protocol deviations will be entered in the CRF and/or documented in monitoring reports.

6.0 TREATMENT OF SUBJECTS

6.1 Drug Preparation and Administration

At the pharmacies, the IMP vials are to be stored at 2-8°C (35.6-46.4°F). At the pharmacies and at the study centers, the prepared APR-246 study product (diluted in sodium chloride solution) is to be stored at not more than 25°C. The infusion should be completed within 24 hours from the time of preparation (see Pharmacy Binder).

APR-246 treatment (Experimental Arm only) will be administered on Days 1-4, and azacitidine on Days **4-10** (Figure 4). Treatment may be administered on an outpatient basis. No investigational or commercial agents or therapies other than those described below may be administered with the intent to treat the patient's disease.

Patients will be randomized (1:1) to 1 of 2 arms, Experimental or Control arm.

6.1.1 Experimental Arm (APR-246 + Azacitidine)

APR-246 will be administered as a 6-hour intravenous infusion daily on days 1-4 of each 28-day cycle. APR-246 fixed dose is 4.5 g. APR-246 is administered in a 2-step infusion:

Step 1: Loading dose of 1.5 g for the first 45 minutes (± 2 min)

Step 2: Maintenance dose of 3 g over 5 hours 15 minutes (± 30 min)

Detailed instructions on vial concentration, preparation and dispensing can be found in the Pharmacy Binder. The infusion timing, including start/stop times and the time of rate change, must be recorded.

Azacitidine will be given at the standard dose of 75 mg/m² SC or IV over 7 consecutive days, Days **4-10**. On **Day 4** azacitidine is administered immediately after the APR-246 infusion. SC method is preferred but IV is allowed at the Investigator's discretion. However, the same route should be maintained over the 7-day treatment period (whichever route is used on Day **4**, the other days should follow the same route of administration). Detailed instructions on preparation and administration can be found in the Pharmacy Binder, current package insert, and in Section 6.1.2, below.

[figure not shown]

Figure 4. Drug Administration Schema for Experimental Arm: APR-246 and Azacitidine

6.1.2 Control Arm (Azacitidine Only)

Azacitidine will be given at the standard dose of 75 mg/m² SC or IV over 7 consecutive days, Days **4-10**, every 28 days. SC method is preferred but IV is allowed at the Investigator's discretion. However, the same route should be maintained over the 7-day treatment period (whichever route is used on Day 4, the other days should follow the same route of administration).

Detailed instructions on preparation and administration can be found in the Pharmacy Binder, and current package insert.

Control Arm: Azacitidine only

[figure not shown]

Figure 5. Drug Administration Schema for Control Arm: Azacitidine Only

6.2 Criteria for Treatment, Retreatment and Dose Modifications

6.2.1 APR-246

This section outlines the requirements for proceeding with treatment with APR-246, and the protocol rules for APR-246 dose modification due to toxicity.

The

Table **4** describes the routine ECG requirements from screening through Cycle 4 for patients in Experimental Arm:

Table 4. ECG Requirements in Experimental Arm

Time Point	ECG, n	Timing
Baseline/Screening	Triplicate	Within 28 days of Cycle 1 Day 1
Cycle 1, Days 1-4	Triplicate	Pre-dose; Post dose (6 hrs. after start of infusion; ± 30 min)
Cycles 2+, Day 1	Triplicate	Pre-dose

At screening (baseline), 12-lead ECGs should be collected in triplicate to confirm QT interval does not exceed 470 msec. QT interval must be calculated from a mean of all three ECG readings using Fridericia's correction ($QTcF = QT/RR^{0.33}$).

During Cycle 1 ECG should be collected in triplicate prior to infusion of APR-246 and at the end of infusion of APR-246 (6 hours after start of infusion, ± 30 min) on Days 1 - 4. QTcF must be calculated from a mean of all three ECG readings to confirm it does not exceed 470 msec.

If a pre-dose ECG shows $QTcF \geq 470$ msec, the QTc reading should be confirmed by manual assessment using Fridericia's correction ($QTcF = QT/RR^{0.33}$). Serum concentrations of electrolytes should be monitored and corrected, if necessary. Additionally, concomitant medication should be reviewed and adjusted, if necessary. ECG may be repeated at any time, including the same day. APR-246 may only be administered when QTcF has returned to < 470 msec. If APR-246 is given on the same day, procedures outlined in the Schedule of Study Evaluations (Table 8) must be followed. If APR-246 cannot be administered on the same day, that dose must be omitted from the cycle.

If there is a significant change in QTcF, defined as either: a) increase > 60 msec from baseline (or pre-dose), or b) increase to an absolute value ≥ 501 msec, i.e. consistent with NCI CTCAE Grade 3 QTc prolongation, QTc prolongation must be confirmed by a manual assessment of the ECG, and using Fridericia's correction ($QTcF = QT/RR^{0.33}$). If confirmed, the therapy should be interrupted until a cause (electrolyte disorders or an effect of a concomitant medication) has been identified and addressed, and QTcF has returned to < 470 msec. If all other causes for clinically significant QT interval prolongation are excluded, APR-246 must be permanently discontinued.

During subsequent cycles ECG should be collected in triplicate prior to infusion of APR-246 on Day 1 of each cycle. QTcF must be calculated from a mean of all three ECG readings to confirm it does not exceed 449 msec. If pre-dose QTcF is 450-469 msec, APR-246 may be administered, and additional triplicate ECG should be performed at the end of infusion (6 hours after start of infusion, ± 30 min). If post-dose ECG shows a significant change in QTcF, defined as either: a) increase > 60 msec from baseline (or pre-dose), or b) increase to an absolute value ≥ 501 msec, i.e. consistent with NCI CTCAE Grade 3 QTc prolongation, QTc prolongation must be confirmed by a manual assessment of the ECG, and using Fridericia's correction ($QTcF = QT/RR^{0.33}$). If confirmed, the therapy should be interrupted until a cause

(electrolyte disorders or an effect of a concomitant medication) has been identified and addressed, and QTcF has returned to < 470 msec. If all other causes for clinically significant QT interval prolongation are excluded, APR-246 must be permanently discontinued. If QTcF is unchanged or there is no significant change, additional ECG is not required during that cycle.

If repeated QTcF measurements show a stable QTcF < 450 msec, or if QTcF remains stable within the interval of 450 – 469 msec with no significant change at the end of infusion during several cycles of treatment, reducing the number of ECGs performed in the study may be discussed with the Medical Monitor.

If a patient starts treatment with another medication known to prolong QT interval at any time during the study therapy, an additional pre- and post-dose (6 hours after start of infusion, ± 30 min) ECG should be performed on the next treatment day. For patients who do not tolerate the protocol-specified dosing schedule, one dose level reduction is permitted (Table 5) in order to allow the patient to continue the study treatment. A second dose reduction could be permitted following discussion with the Sponsor and Medical Monitor.

Table 5. APR-246 Dose Levels

Dose Modification	APR-246 Dose
Starting Dose Level (DL)	APR-246 4.5 g/day 1.5 g (for first 45 minutes) + 3.0 g (for 5 hours 15 minutes)
One dose level reduction (DL-1)	APR-246 4.0 g/day 1.33 g (for first 45 minutes) + 2.67 g (for 5 hours 15 minutes)
Second dose level reduction (DL-2)*	APR-246 3.5 g/day 1.16 g (for first 45 minutes) + 2.34 g (for 5 hours 15 minutes)

* Discuss with Sponsor and Medical Monitor before implementing second dose level reduction. The rationale behind this dose reduction scheme is the steep relation between C_{max} and dose, e.g. the suggested 11% and 22% reductions in dose result in 19% and 33% lowering of the average C_{max}, respectively

All dose modifications, interruptions or discontinuations must be based on the worst preceding toxicity as graded by the NCI Clinical Toxicity Criteria (NCI-CTCAE version 5). Once a dose has been reduced during a treatment cycle, re-escalation during subsequent cycles may be permitted following discussion with the Medical Monitor. If the administration of

APR-246 is interrupted for reasons other than toxicity, then treatment with APR-246 may be resumed at the same dose. The same provision applies if the patient experienced an unacceptable toxicity not specifically described in Table 6, provided that this toxicity resolved to \leq Grade 1, unless otherwise specified.

Following 4 cycles of therapy for responding patients (i.e. CR, PR, HI, mCR with HI, mCR without HI) treatment with APR-246 and azacitidine can be delayed for up to 14 days to allow for count recovery at Investigator discretion pending discussion with the Sponsor and Medical Monitor.

Non-hematologic Grade 4 treatment related adverse events will lead to permanent discontinuation, irrespective of recovery time, unless otherwise specified. Exceptions would include nausea/vomiting/diarrhea which can be controlled by medications and/or asymptomatic electrolyte imbalances which can be corrected. In addition, in most instances, patients that experience a prolonged treatment interruption because of an adverse event and/or a Grade 3 adverse event will decrease the dose of study drug after their recovery (see specific tables for dose adjustment guidelines).

If any drug-related Grade 3 or 4 toxicity that is not clearly related to azacitidine is observed, APR-246 dose must be reduced for the next and subsequent cycles.

Patients requiring >2 dose reductions for APR-246 will be permanently discontinued from study drug. Patients who permanently discontinue APR-246 or azacitidine should have follow-up within 28 days after discontinuation of all study treatment or resolution of the AE to \leq Grade 1, whichever occurs first, that includes all study assessments appropriate to monitor the event.

Table 6. Recommendations for APR-246 Dose Modifications and Criteria for Treatment Interruption and Re-Initiation with Treatment-Related Adverse Events

Any changes in dose must be recorded on the Dosage Administration Record CRF.

Renal Toxicities

Parameter	Worst toxicity [†]	Dose Modifications for APR-246
Serum Creatinine	Grade 1 (< 1.5 × baseline)	Maintain dose level
	Grade 2 (> 1.5 to 3.0 × baseline)	Omit dose until resolved to ≤ Grade 1, then: If first occurrence, then maintain dose level If second or more consecutive occurrence, then ↓ 1 dose level
	Grade 3 (> 3.0 – 6.0 × baseline)	Omit dose until resolved to ≤ Grade 1, then: ↓ 1 dose level If not resolved or resolved in > 7 days, evaluate if other contributing factors are present. If none, or after consideration of best interest of the patient, discontinue patient from APR-246. If other factors present, consider continuing after ↓ 1 dose level
	Grade 4 (> 6.0 × baseline)	Permanently discontinue patient from APR-246
† Common Terminology Criteria for Adverse Events (CTCAE) version 5.		

Hepatic Toxicities[◇]

Parameter	Worst toxicity	Dose Modifications for APR-246
Bilirubin [‡]	Grade 1 (> ULN - 1.5 × ULN)	Maintain dose level with LFTs [‡] monitored as per protocol
	Grade 2 (> 1.5 - 3.0 × ULN) with ALT or AST ≤ 3.0 × ULN	Omit dose until resolved to ≤ Grade 1, then: If resolved in ≤ 7 days, if first occurrence, then maintain dose level If second or more consecutive occurrence or if resolved in > 7 days, then ↓ 1 dose level
	Grade 3 (> 3.0 - 10.0 × ULN) with ALT or AST ≤ 3.0 × ULN	Omit dose until resolved to ≤ Grade 1, then: If resolved in ≤ 7 days, ↓ 1 dose level. If no subsequent event, consider re-escalation to original dose level. Omit dose until resolved to ≤ Grade 1, then: ↓ 1 dose level. If second or more consecutive occurrence or if not resolved or resolved in > 7 days, evaluate if other contributing factors are present. If none, or after consideration of best interest of the patient, discontinue patient from APR-246. If other factors present, consider continuing after ↓ 1 dose level.
	Grade 4 (> 10.0 × ULN)	Permanently discontinue patient from APR-246

Parameter	Worst toxicity	Dose Modifications for APR-246
AST or ALT	Grade 1 (> ULN - 3.0 × ULN if baseline was normal; 1.5 - 3.0 × baseline if baseline was abnormal)	Maintain dose level with LFTs [‡] monitored per protocol
	Grade 2 (> 3.0 - 5.0 × ULN if baseline was normal; >3.0 - 5.0 × baseline if baseline was abnormal) in the absence of total bilirubin elevation to > 2.0 × ULN	Omit dose until resolved to ≤ Grade 1, then If resolved in ≤ 7 days, if first consecutive occurrence, then maintain dose level If second or more consecutive occurrence or if resolved in > 7 days, then ↓ 1 dose level
	Grade 3 (> 5.0 - 20.0 × ULN if baseline was normal; > 5.0 – 20.0 x baseline if baseline was abnormal) in the absence of total bilirubin elevation to > 2.0 × ULN	Omit dose until resolved to ≤ Grade 1, then If resolved in ≤ 7 days, if first consecutive occurrence, then maintain dose level. If second or more consecutive occurrence or if not resolved or resolved in > 7 days, evaluate if other contributing factors are present. If none, or after consideration of best interest of the patient, discontinue patient from APR-246. If other factors present consider continuing after ↓ 1 dose level
	Grade 4 (> 20.0 × ULN if baseline was normal; > 20.0 × baseline if baseline was abnormal)	Permanently discontinue patient from APR-246

◊ Please note that the Investigator is responsible for determining whether a patient meets potential Hy's Law (PHL) criteria at any point during the study. Hy's law identifies patients at risk for severe drug-induced liver injury, DILI, and is defined as AST or ALT ≥ 3× ULN together with Total Bilirubin Level ≥ 2×ULN, where no other reason, other than the suspected drug, can be found to explain the combination of increases, eg, elevated ALP indicating cholestasis, viral hepatitis, or another drug.

† Common Terminology Criteria for Adverse Events (CTCAE) version 5.

‡ For patients with Gilbert's syndrome, these dose modifications apply to changes in direct bilirubin only.

* LFTs include albumin, ALT, AST, total bilirubin (fractionated if total bilirubin > 2.0 × ULN), alkaline phosphatase.

Hematological Toxicities[†]

Parameter	Worst toxicity	Dose Modifications for APR-246
Febrile neutropenia	ANC < 0.5 × 10 ⁹ /L, temperature of ≥ 38 °C or a sustained temperature of ≥ 38°C for more than 1hour	Omit dose until resolved to ≤ Grade 1, then ↓ 1 dose level
Thrombocytopenia	Grade 4 (PLT < 25 × 10 ⁹ /L) [‡] and major bleeding event	Permanently discontinue patient from APR-246

† Only applicable for patients with normal baseline absolute neutrophil count (ANC) and platelets. For patients with low (abnormal) baseline ANC and/or platelets that do not return to baseline (pre-cycle) after a clinically significant decrease following treatment, please contact the Medical Monitor.

‡ Common Terminology Criteria for Adverse Events (CTCAE) version 5.

Other Non-Hematological Toxicities

Parameter	Worst toxicity	Dose Modifications for APR-246
CNS – dizziness, dyskinesia and ataxia	Grade 1	Maintain dose level
	Grade 2	If resolved (to ≤ Grade 1) with medical therapy, continue same dose level If not resolved despite treatment interruption and maximal medical therapy, stop infusion and ↓ 1 dose level for subsequent dose
	Grade 3	Stop infusion and give medical therapy. If resolved (to ≤ Grade 1) with medical therapy, infusion may continue at the investigator’s discretion. ↓ 1 dose level for subsequent dose
	Grade 4	Permanently discontinue patient from APR-246.
Infusion Related Reaction	Grade 1	Maintain dose level.
	Grade 2	Maintain dose level; Symptomatic management (e.g., antihistamines, corticosteroids, narcotics, IV fluids)
	Grade 3	If resolved (to ≤ Grade 1) in < 4 hours with treatment interruption and medical therapy (e.g., antihistamines, corticosteroids, narcotics, IV fluids), continue same dose level and rate. If not resolved in < 4 hours despite treatment interruption and maximal medical therapy, stop infusion and ↓ 1 dose level for subsequent dose
	Grade 4	Permanently discontinue patient from APR-246.
Nausea/Vomiting/ Diarrhea	Grade 1	Maintain dose level
	Grade 2	If resolved (to ≤ Grade 1), then maintain dose level If not resolved despite maximal medical therapy, then ↓ 1 dose level
	Grade 3	If resolved (to ≤ Grade 1), then maintain dose level If not resolved despite maximal medical therapy, then ↓ 1 dose level
	Grade 4	Permanently discontinue patient from APR-246
Any Other Toxicity	Grade 3 or 4	Delay dose until resolution to ≤ Grade1, then ↓ 1 dose level

† Common Terminology Criteria for Adverse Events (CTCAE) version 5.

Treating physicians should use clinical judgment and may consult the Medical Monitor for guidance with dose modifications.

